7.2 PARTICIPANT DISCONTINUATION/WITHDRAWAL FROM THE STUDY

Prior to removal from study, effort must be made to contact all study participants via telephone to determine safety regarding the intervention approximately 2-4 weeks following the last dose of study therapy.

Participants are free to withdraw from participation in the study at any time upon request.

An investigator may discontinue or withdraw a participant from the study for the following reasons:

- Significant study intervention non-compliance
- If the participant meets an exclusion criterion (newly developed) that precludes further study participation
- Subject has completed the study follow-up period

- Screen Failure

The reason for participant discontinuation or withdrawal from the study will be recorded on the Case Report Form (CRF). Subjects who sign the informed consent form and are randomized but do not receive the study intervention may be replaced. Subjects who sign the informed consent form, and are randomized and receive the study intervention, and subsequently withdraw, or are withdrawn or discontinued from the study, will not be replaced.

7.3 LOST TO FOLLOW-UP

A participant will be considered lost to follow-up if he or she fails to return for the admission following the screening visit and is unable to be contacted by the study site staff.

The following actions must be taken if a participant fails to return to the clinic for a required study visit:

- The site will attempt to contact the participant and reschedule the missed visit over the course of the following one week and counsel the participant on the importance of maintaining the assigned visit schedule and ascertain if the participant wishes to and/or should continue in the study.
- Before a participant is deemed lost to follow-up, the investigator or designee will make every effort to regain contact with the participant (where possible, 3 telephone calls and, if necessary, a certified letter to the participant's last known mailing address or local equivalent methods). These contact attempts should be documented in the participant's medical record or study file.
- Should the participant continue to be unreachable, he or she will be considered to have withdrawn from the study with a primary reason of lost to follow-up.

8 STUDY ASSESSMENTS AND PROCEDURES

8.1 SCREENING PROCEDURES

Recruitment will occur from existing cohort of PD patients that have enrolled in NIH protocols 01-N-0206, 93-N-0202, and 14-N-0086. All informed consent documents associated to the referenced protocols contains language that obtains permission from subjects for their information to be saved and to be re-contacted by study investigators for future research studies at the NIH. There will be access to prior records in CRIS, paper chart, and genetic testing. The data are accessible by associate investigators of all the above protocols. All federal and state laws as well as requirements of the NIH will be followed regarding patients' PHI.

Participants either previously seen under the protocols listed above, or otherwise contacted or who contact study investigators with interest in the study will be pre-screened with the request for /in most cases

Abbreviated Title: Tolerability and efficacy of ketogenic diet in Parkinson's Disease

Version Date: 04/19/2021

obtaining outside documentation of Parkinson's Disease clinical care, with exception being made only if the records are not available upon request, however a thorough attempt will be made at verification of existing diagnosis. These outside documents will be requested of participants to be faxed to the Study Investigator (PI), or permission be granted for PI to request this from the participant's physician office directly. For participants pre-screened who have participated in 01-N-0206, prior documentation by the protocol investigators will likely be considered to be sufficient without outside documentation.

At the screening visit after participant's informed consent is obtained, data will also be obtained from patient self-report, however effort will be made to verify this with physician or ancillary medical care documentation.

8.2 EFFICACY ASSESSMENTS

As one of the study aims is to determine feasibility of MCT supplemented ketogenic diet, the efficacy of primary objective of study feasibility as per recruitment, retention, acceptability, and adherence will be determined by a composite outcome, in which all criteria are met: completion rate of both inpatient 1 week and outpatient 2 week segments, with target of >80% for each; recruitment target of 32 participants reached; adherence to outpatient diet with mean daily carb $\leq 10\%$; intervention is acceptable to all participants by Likert scale $\geq 2/4$ of likelihood of using this therapy in the future and effectiveness in symptom reduction.

Efficacy of secondary objective of TUG reduction will be assessed by between-group mean difference at 7 days (MCT-KD vs. SAD). It is presumed that the standard (control) diet will not provide any issues of feasibility. Refer to Section 4.1 Study Design for direct and indirect determinations of ketosis.

Timed Up & Go (TUG)

Efficacy of TUG will also factor effect of time, via repeated measures ANOVA for TUG that will be tested three times per session and fastest time used, with same timing relation to dopaminergic medications.

Efficacy will be tested further in the between group difference between the two diets on outcomes of the following, again with same timing regarding dopaminergic medications:

Exploratory measures will be done as per test schedule in Section 4.1, generally once daily or less.

Stroop Word-Color Interference

this test has been shown to be impaired in PD as part of the executive network of actively choosing the stimulus while inhibiting the background. The latency will be determined from a computer test.

N-Back Task (% correct)

This test (Kirchner, 1958) involves a series of visual stimuli such as letters, and then participants are asked if each stimulus matches a stimulus n trials before. Performance is shown to be impaired in PD to a greater degree than in normal aging

Simple Reaction Time (SRT)

SRT (same cue on computer screen, press button; machine is used already for Chronic Fatigue Syndrome protocol studies and will be made available for the study). PD is consistently shown to have increased latency that is attributed to the akinesia as cardinal motor symptom. The increase in latency is reduced by

Abbreviated Title: Tolerability and efficacy of ketogenic diet in Parkinson's Disease

Version Date: 04/19/2021

Levodopa therapy (Muller 2001, 23729617), relatively unaffected by repetition / motor learning, and is hypothesized also to improve with metabolic ketosis.

Keyboard MN and PQ speed and rhythm analysis

The Keyboard test is used already for the SCA7 protocol by Human Motor Control neurophysiologist and will be made available for the study. Rhythm can be obtained from the raw data, which imputes the time of the keystroke into a text document and can be analyzed in frequency vs. speed analysis. PD bradykinesia involves a sequence effect of both reduction in amplitude and speed of repetitive fine motor movements that is well established. Therefore, as speed decreases there is expected greater variability in frequency).

9-hole pegboard test

This standardized, quantitative test of finger dexterity has been studied in Parkinson's Disease (e.g. Earhart 2011) and found to correlate with Hoehn & Yahr disease severity with times of 20s for stage I ranging to 40s for stage IV. It can be done with a single investigator, stopwatch on a table, and the equipment is already available (being used for Neuro testing in 7SW for SCA7).

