3. OBJECTIVES AND ENDPOINTS

OBJECTIVES	OUTCOME MEASURES	JUSTIFICATION FOR ENDPOINTS
Primary		
Feasibility of MCT-KD x three weeks	Composite outcome (all of the following measures must be met):	MCT-KD has never been studied in PD population (expected to

Abbreviated Title: Tolerability and efficacy of ketogenic diet in Parkinson's Disease**Version Date:** 04/19/2021

	
1) Recruitment reaches target of 32 participants or as per pre-set interim analysis
 
2) Study retention rate >80% of all participants at 3 weeks
 
3) Adherence ($\leq 10\%$ mean daily energy from net carb over 2 weeks MCT-KD outpatient, assessed by 2x/week unscheduled phone calls by CC Nutrition staff)
 
4) Acceptability – Likert scale ≥ 2 (at least somewhat likely to use diet in future and at least somewhat effective in improving PD symptoms) at end of study (week 3)
	augment ketosis) and feasibility has not been established.
Secondary		
Timed Up & Go (TUG) time, mean difference between groups on study day 7	Mobility on the Timed Up and Go (TUG) test, daily (fastest of three trials per session) units: seconds Range: 8-18s	TUG time is generally regarded as an index of fall risk – estimated 20% risk reduction with 4s faster time (Nocera et al, 2013)
Tertiary/Exploratory		

Nutritional ketosis (NK) improves PD symptomatology at three weeks in the following: in cognition (improved attention, recall, and executive function), and motor function (reduced akinesia and tremor). A low fat (standard American) diet (SAD) does not.
 
NK reduces non-motor symptoms, subjective motor fluctuations and daily off time within the immediate keto-induction period, while SAD does not (mean difference at 1
	
Stroop word-color interference latency (unit: ms, range: 110-135 ms), 0,1,2,3 back recall task (unit i: % error of missing true n-back letter presented; range i: 0-back 0-10%, 1-back 4-20%, 2-back 15-30%, 3-back 20-32%; unit ii reaction time (RT) ms, range ii 0-back 500-740 ms; 1-back 600-980 ms; 2-back 700-1200 ms; 3-back 700-1200 ms); fingertap speed and rhythm (MN and PQ keyboard tasks; units MN and PQ keystroke speed, in keys/s; range MN
	
All of these tests have been shown to be impaired in PD cohorts and are at least semi-quantitative and amenable to serially repeated measures with good test-retest reliability
 
Scalp EEG is non-invasive, easy to perform in the setting of intervention, and as

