The interventional food-based product, Liquigen® (KetoCal), will be administered by NIH CC Nutrition staff to MCT-KD group participants as per defined blinded diet.

Primary Outcome: feasibility will be assessed in a composite fashion by retention rate >80% at study end (week 3) ; study adherence in the outpatient segment defined by maintaining mean carbohydrate limit ≤ 10%, as by CC nutrition staff twice weekly unscheduled calls data input to online application); reaching recruitment target of 32 participants, unless otherwise defined by interim analysis (see Section 9); and acceptability by likelihood to use the diet in the future and effectiveness in reducing PD symptoms both “somewhat” ≥ 2/4 on Likert scales. All criteria must be met.

Secondary outcome: Timed Up & Go (TUG) time at between MCT-KD and SAD groups mean difference on inpatient day 7.

Exploratory outcomes:

Effort will be taken in establishing medication and testing schedules, for outcomes to be assessed at the same time from last dopaminergic medications and other psychotropic medication administrations including cholinergic and muscle relaxants (see table 2). All exploratory outcomes will be assessed pre (admission day 1) and post (day 7 and week 3) diet intervention. Additionally, reaction time, Stroop test, N-back test, MN/PQ fingertapping tests, 9-HPT, UPDRS-3, and resting HRV will be tested daily on admission days 2-6.

Stroop word color interference latency (Stroop test B), N-back test (3-back letter), MN and PQ keystroke tasks, tremor accelerometry, 9-hole pegboard test (9-HPT), and simple reaction time (SRT), EEG waveform analysis (steepness ratio, sharpness ratio, modulation index), and quantitative (q)EEG assessment; daily assessments of heart rate variability (SDNN, pNN50, rMSSD, power spectral analysis), and supine to standing blood pressure and heart; resting heart rate (5 min recordings daily), UPDRS including daily UPDRS-3, daily ON time, daily PD symptoms, daily keto-induction symptoms, pre vs. post intervention Non-Motor Symptom Severity Score (NMSS)

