1 STATISTICAL CONSIDERATIONS

9.1 STATISTICAL HYPOTHESIS

Primary hypothesis:

Nutritional ketosis supplemented by MCT oil is feasible within a Parkinson Disease cohort as defined by an acceptable retention rate and outpatient adherence.

Primary outcome: Feasibility of nutritional ketosis(ketogenic diet with 80% lipid including MCT oil, 10-15% protein, 5-10% carbohydrate), in Parkinson Disease cohort defined as a composite outcome meeting all of the following criteria: recruitment target of 32 or as per interim power analysis defined in Section 9.4.6; retention rate > 80% at study end; adherence to ketogenic diet in the outpatient portion defined as mean carbohydrate energy intake <10%, and intervention is acceptable to all participants by Likert scale \geq 2/4 of likelihood of using this therapy in the future and effectiveness in symptom reduction, from all study participants at 3 weeks.

Secondary hypothesis:

Abbreviated Title: Tolerability and efficacy of ketogenic diet in Parkinson's Disease

Version Date: 04/19/2021

Nutritional induced ketosis (NK) increases mobility based on TUG score in a Parkinson Disease cohort at 7 days compared to usual diet (35% lipid, 10-15% protein, 50-55% carbohydrate). Secondary outcome: timed Up & Go test (TUG score) at study day 7 (fastest of three trials)

$H_0: \mu_1 = \mu_2$, where μ_1 and μ_2 are the population means for the NK diet group and usual diet group respectively vs. $H_1: \mu_1 \neq \mu_2$.

Exploratory hypotheses:

Hypothesis A: Nutritional ketosis improves PD symptomatology in cognition (improved attention, recall, and executive function, and motor function akinesia and tremor within six days, as assessed by: Stroop word-color interference latency (executive function), n-back recall task (attention and working memory), simple reaction time (akinesia); fingertap speed and rhythm MN and PQ keyboard tasks (fine motor), and autonomic function (heart rate variability at rest and with deep breathing / Valsalva Maneuver tests)

Hypothesis B: The mechanism of symptomatic reduction of NK in PD is both augmented mitochondrial metabolism (direct, rapid) and augmented neurotransmitter and growth factor synthesis (indirect, delayed), especially GABA and dopamine, as assessed by resting state EEG spectral power, phase coherence, and M1 waveform normalization. Accordingly, effect sizes for exploratory outcomes will be greater at 3 weeks than 7 days.

Exploratory outcomes daily (days 1-7), week 3

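### The all-criteria-must-be-met feasibility outcome needs, on its literal wording, every participant to find the diet acceptable, and no section states a proportion, a denominator or a missing-survey rule

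*Combined protocol and SAP*

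**What the plan says.** Sections 3, 4.1, 8.2 and 9.1 all define feasibility as a composite that succeeds only if every criterion is met: recruitment, retention, adherence and acceptability.

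**Acceptability**
- Sections 8.2 and 9.1: the "intervention is acceptable to all participants by Likert scale" at 2/4 or more, for likelihood of future use and for effectiveness. Section 9.1 closes its definition with "from all study participants at 3 weeks".
- Section 3: a score of at least 2, glossed as "at least somewhat likely to use diet in future and at least somewhat effective in improving PD symptoms". It does not say how participants are combined.
- Section 4.1, Primary Outcome: the same cut-off on both items, again with no combining rule.
- Section 1.1: names the week-3 exit survey but gives no cut-off. It describes the scales as four-point, whereas the exit-survey entry in 4.1 gives them as 0 to 4, which is five values.

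**Retention**
- Section 8.2 (1.1 is similar): "completion rate of both inpatient 1 week and outpatient 2 week segments, with target of >80% for each".
- Section 3: "Study retention rate >80% of all participants at 3 weeks". Sections 4.1 and 9.1 also use one rate at study end.

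**Analysis**
- Section 9.4.1 says only that feasibility will be assessed descriptively. No section says how a missing exit survey is treated.

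**The concern.** With no inferential test planned, the written cut-offs are the entire decision rule for the primary outcome. On the literal wording of 8.2 and 9.1, that rule is unanimity on two items. The composite would tolerate losing up to 6 of 32 participants (26/32 = 81.25%) but not one low rating among those who stay. A diet accepted by 25 of 26 completers would fail even with recruitment, retention and adherence all met.

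If unanimity is not what is meant, the rule is undefined. A mean, a median or a proportion could each be chosen after the ratings are known, and they can give different answers. The same holds for participants with no week-3 survey: if they belong to the group that must all accept, any dropout could fail acceptability, although the retention criterion allows some loss.

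**Working it through.** **1. The plan's own figure.** The documents give no operating figure for the composite. The only related number is the sample size in 9.2, which is based on TUG. Inputs: difference 4.5 s, SD 4 s (standardised difference 4.5/4 = 1.125), two-sided alpha 0.0492. Two-sample t-test power from the noncentral t is 0.784 at 13 per group and 0.815 at 14 per group, so 14 per group, 28 in all. With 10% dropout, 28/0.9 = 31.1, or 32 in two equal groups. The figure reproduces, but feasibility did not enter it.

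**2. Number of raters.** The fewest completers that exceed 80% of 32 is 26 (25/32 = 78.1%, 26/32 = 81.25%). At the planned 10% dropout, about 29 complete (32 × 0.9 = 28.8).

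**3. Literal rule.** Let p be the chance that one participant scores 2 or more on both items. It is an assumption, shown as a range, with independence between participants. The chance that all n accept is p^n.

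| p | n = 26 | n = 29 |
|---|---|---|
| 0.90 | 0.065 | 0.047 |
| 0.95 | 0.264 | 0.226 |
| 0.99 | 0.770 | 0.747 |

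For an 80% chance of passing, p must be 0.8^(1/26) = 0.9915 with 26 raters, or 0.8^(1/29) = 0.9923 with 29.

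**4. One data set, three rules.** Take 26 raters: 25 score 3 on both items and one scores 1. Unanimity fails. A mean rule passes: (25 × 3 + 1)/26 = 2.9. A rule of more than 80% passes: 25/26 = 96%.

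**5. A proportion rule, for comparison.** More than 80% of 26 responders means at least 21 (21/26 = 80.8%). The exact binomial chance of passing is 16%, 58%, 96% and 99.8% at p = 0.70, 0.80, 0.90 and 0.95.

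**6. The denominator matters.** The same 21 acceptances are 21/32 = 66% of those randomised. Conversely, more than 80% of all 32, with missing surveys counted as not acceptable, needs 26 acceptances. With only 26 responders that is unanimity again; with 29 responders it is 26 of 29. The threshold and the denominator therefore have to be chosen together.

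**7. Retention wording.** If outpatient completion is counted among those who enter that segment, 26/32 then 21/26 meets the segment rule with 21/32 = 66% at week 3, which fails section 3. If both segments use all participants and completion is nested, the two rules agree. Under the conditional reading, with 32 participants and 10% total loss, the chance that the segment rule passes and the week-3 rule fails is 3.3% with loss split evenly, 2.1% with 98% inpatient completion, and 0 if all loss falls in one segment.

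**The case against.** The best case for the plan is that the phrase refers to both original arms and not to every individual. Everyone receives the ketogenic diet at home (4.2), the two groups become one diet group by week 3 (1.1), and 9.1 ends with "from all study participants at 3 weeks". This reading is plausible. It does not supply a rule, because pooled ratings still need a mean or a proportion and none is written.

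A reader might also infer that the sections contradict each other on acceptability. They do not: 3 and 4.1 are silent on combining participants, and silence is an omission, not a rival rule. How strict a go/no-go criterion should be is partly the sponsor's choice.

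The size of the effect rests on assumed acceptance rates. The range of 90% to 99% is where unanimity and a proportion rule differ most. At 70% acceptance unanimity is almost certain to fail and the illustrative rule of more than 80% passes only 16% of the time, so the two largely agree.

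The retention difference is tempting to present as a second conflict. No section states the conditional denominator that it needs. Section 3 names all participants, and on that basis the rules agree when completion is nested. A conflict in the other direction would need completion to mean staying on the home diet; but adherence is a separate component, and 7.1 distinguishes stopping the diet from leaving the study. It is a harmonisation item and no more.

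Finally, this is a descriptive pilot sized on TUG, and 9.2 says that feasibility is not what justifies the study. That limits the consequence but does not remove the need for a defined primary outcome.

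**Conclusion.** The point stands as a defect in the definition of the primary outcome. Sections 8.2 and 9.1, read literally, let one low score fail an all-or-nothing composite. Read otherwise, the acceptability criterion has no combining rule, and under either reading missing surveys are not covered. On the literal reading, 26 completers pass with probability 6.5%, 26% or 77% at assumed independent individual acceptance of 90%, 95% or 99%.

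A reader might go further and conclude that the primary outcome is certain to fail, or that the trial cannot proceed without this change. The documents do not support that. They give no acceptance rate, the pooled-arms reading is open, the primary analysis is descriptive, each component can be reported separately, and the TUG analysis does not depend on it. The change should be made; it is not a condition for the trial's validity.

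**What to change.** - **Acceptability.** In 1.1, 3, 4.1, 8.2 and 9.1, replace the requirement on all participants with one prespecified proportion scoring 2 or more on both items. The sponsor chooses the value.
- **Denominator and missing surveys.** State in advance who is counted, and whether a missing week-3 survey counts as not acceptable in the deciding analysis, not only in a sensitivity count. If responders are the denominator, say so and report the proportion of all randomised beside it. Choose the threshold with the denominator in view (step 6 of the working).
- **Scale.** Check the four-point and 0-to-4 descriptions against the actual survey and use one coding, since it determines what a score of 2 means.
- **Retention, minor.** Use one rule of more than 80% at week 3 with all randomised participants as denominator, as section 3 already implies, and report completion of each segment descriptively so that the inpatient and outpatient comparison in 4.2 is kept.

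The cost is protocol wording only, with no new procedures and no change in sample size. The trade-off is that acceptability becomes less strict than unanimity.

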Specific to participants who are hypertensive or diabetic, ketogenic diet is generally regarded as safe and beneficial in lowering blood pressure and fasting blood sugar levels. However, there can be risk if this occurs and medication is not adjusted due to overshoot of therapeutic effect. Risk will be mitigated by excluding uncontrolled hypertension defined as SBP > 180 or DBP > 105, and uncontrolled diabetes (A1c > 8.0%) and monitoring blood pressure and blood glucose levels frequently, with potential reduction of glucose or blood pressure lowering medication as per discretion of those study investigators who are licensed physicians credentialed at the NIH Clinical Center.

Other procedures and measurements (venous blood draws, motor physiology, cognition, EEG recording) are expected to incur minimal risk similar to what is encountered in routine clinical evaluation.

c. Risks of neurologic examination:

There is minimal risk associated with a routine physical and neurologic examination or with PD screening questionnaires.

d. Risks of surface ECG:

Risk of skin irritation at the site of the ECG electrode may be minimal in some subjects. There is minimal risk associated with surface ECG.

e. Risks of EEG:

There is minimal risk concerning the EEG technique itself. The electrode cap can be uncomfortably tight. There may be mild irritation of the skin and scalp from the mild abrasion needed to assure good contact or from the collodion, paste, or gels used.

-if participant decides not to perform in any measurements, they will not be per se removed from the study. Options include re-testing at a later time and omitting specific declined tests.

f. Risks of video recording:

There is minimal risk to patient confidentiality. This is because video will be done only with participant's signed informed consent, including option to blur facial features. Video will be taken by NIH issued video camera kept locked in the office, and files will be transferred to secure NIH server for later review by a separately blinded rater. Videos may be viewed for official NIH teaching / educational purposes within NIH staff. Any external sharing such as for academic conference presentation will be done only with participants' written informed consent.

g. Risks of Blood Draw

There is minimal risk of bruising or prolonged bleeding from phlebotomy; local pain and fainting or infection at the needle entry site are possible but rare side effects.

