9.4.2 Analysis of Secondary Endpoint

To evaluate the diet effect on the TUG score, analysis of covariance (ANCOVA) will be performed with age and TUG score at day 1 as covariates, and TUG score on day 7 as a dependent variable.

Repeated measures ANCOVA with age as a covariate will also be performed to evaluate the within-subject effect: baseline day 1 vs. day 7 (inpatient) vs. 3 weeks (outpatient) of the intervention, and between subject-effect (diet): ketogenic diet vs. standard American diet.

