9.4.3 Analysis of the Exploratory Outcomes

ANCOVA will be also used to examine the diet effect on the other exploratory outcomes, where each outcome measure over time will be used as a dependent variable with age and the outcome at day 1 as covariates.

Longitudinal analysis methods, such as repeated measures ANCOVA, random coefficient model or mixed model, will be used to examine the change in the exploratory outcomes over the six days. Within-subject

Abbreviated Title: Tolerability and efficacy of ketogenic diet in Parkinson's Disease

Version Date: 04/19/2021

(mixed model) and across-subject (spearman or Pearson) correlation analysis will be applied to evaluate the relationship between outcome variables.

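### The supporting repeated-measures analysis of TUG (day 1, day 7, week 3) would, in its classical form, discard the day-1 and day-7 data of anyone without a usable week-3 value

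*Combined protocol and SAP*

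**What the plan says.** The plan has two layers of TUG analysis.

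- **Main secondary analysis (9.4.2).** Day-7 TUG is the dependent variable, and "analysis of covariance (ANCOVA) will be performed with age and TUG score at day 1 as covariates". It uses nothing after day 7.
- **Time-course analysis (8.2 and 9.4.2).** Section 8.2 states "Efficacy of TUG will also factor effect of time, via repeated measures ANOVA for TUG that will be tested three times per session" but lists no sessions. Section 9.4.2 states "Repeated measures ANCOVA with age as a covariate will also be performed to evaluate the within-subject effect" and defines it as "within-subject effect: baseline day 1 vs. day 7 (inpatient) vs. 3 weeks (outpatient) of the intervention", with diet as the between-subject factor.

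For the exploratory outcomes, 9.4.3 is broader: "Longitudinal analysis methods, such as repeated measures ANCOVA, random coefficient model or mixed model, will be used". It lists repeated-measures ANCOVA and the mixed model as different options. Neither 8.2 nor 9.4.2 gives TUG the second option.

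Section 9.3 only names the 32 randomised participants, and no section gives a missing-data rule for TUG. Several sections nevertheless allow for gaps:

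- Section 2.3.1, on participants who decline a measurement: "Options include re-testing at a later time and omitting specific declined tests".
- Section 6.4 accepts that a participant may decline the outpatient part.
- Section 7.2 does not replace people who withdraw after starting the intervention.
- Section 6.1.1 flags week-3 visits that miss the two-week date for separate handling, without saying whether they enter the model.
- Section 9.2 allows for 10% dropout, and Section 3 counts retention above 80% as success.

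**The concern.** Classical repeated-measures ANOVA or ANCOVA works on complete sets of sessions. Under the three-session model in 9.4.2, someone who finishes the inpatient week and then skips week 3, or returns off schedule and is set aside, contributes nothing. Their day-1 and day-7 values exist, but this test ignores them.

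Two things are at stake. The first is precision, in a trial of 32. The second is selection: completers may differ from leavers. Section 2.3.2 reports that in an earlier ketogenic trial in PD, subjective tremor or rigidity accounted for half of the four ketogenic-arm dropouts, so motor-related loss is plausible. This is the only stated TUG analysis that uses week 3, and the time course is one of the trial's stated interests.

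**Working it through.** **Inputs.** Difference 4.5 s, SD 4 s, alpha 0.0492, 14 per group, 10% dropout, 32 recruited (9.2); two-sided alternative (9.1); retention above 80% at three weeks (Section 3); modelled sessions day 1, day 7 and week 3 (9.4.2).

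**Step 1: the plan's own figure.** Power of a two-sample t-test from the noncentral t distribution, with noncentrality 4.5 / (4 × sqrt(2/n)) and n per group:
- n = 13 gives 78.4%.
- n = 14 gives 81.5%, so 14 is the smallest n reaching 80%.
- With 10% dropout, 14 / 0.90 = 15.6, rounded up to 16 per group, or 32 in total.

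The sample size reproduces and is not in dispute.

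**Step 2: participants with all three sessions.**
- Planned dropout: 32 × 0.90 = 28.8.
- Lowest passing retention: 25/32 = 78.1% fails and 26/32 = 81.25% passes, so 26 remain and 6 (19%) are lost.

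**Step 3: effect on the standard error.** For a difference between two equal groups totalling N, SE = 2 × SD / sqrt(N). Relative to all 32, the ratio is sqrt(32/N), whatever the SD.

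| Complete sets | SE at SD 4 s | Ratio to N = 32 |
|---|---|---|
| 32 | 8/5.657 = 1.414 s | 1.000 |
| 28.8 (10% dropout) | 8/5.367 = 1.491 s | 1.054 |
| 26 (lowest passing) | 8/5.099 = 1.569 s | 1.109 |

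This assumes even loss across arms and that everyone lost has day-1 and day-7 values. A mixed model would recover all of this loss at day 7. At week 3 it would recover only part, depending on the within-participant correlation, which the plan does not give.

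**Step 4: missed day-1 or day-7 tests.** If 2% of inpatient sessions were also missed (assumed; range 0% to 5%), complete sets at 10% dropout would be 32 × 0.90 × 0.98² = 27.7, with a range from 28.8 down to 32 × 0.90 × 0.95² = 26.0. This extra loss would also affect the day-7 ANCOVA, so it is not specific to the repeated-measures model.

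**Step 5: direction of any selection bias.** With no true effect, the completers-only bias is the shift in the ketogenic-arm completers' mean minus the shift in the control-arm completers' mean. Equal informative loss in both arms cancels. More in the ketogenic arm favours the ketogenic diet, and more in the control arm does the reverse. After day 7 both arms take the ketogenic diet at home, and controls start it then. The plan's text therefore does not fix the sign.

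**The case against.** The strongest reply is that this is a supporting test and little is lost. Most of that stands:

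- The powered day-7 ANCOVA keeps anyone with day-1 and day-7 data, whether or not they return.
- Casewise deletion is a default of the classical method and is not prescribed anywhere in the plan.
- The plan works to limit gaps. Re-testing is offered for declined tests (2.3.1), people who stop the diet still complete the study procedures (7.1), and missed visits are to be rescheduled (7.3).
- The earlier PD attrition figures in Table 1 (28% and 18%) come from 28-day and 8-week studies, and only 9% in the latter was attributed to diet.

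This limits the size of the problem but does not remove it. A rescheduled week-3 visit may fall off the two-week date, and 6.1.1 leaves its place in the analysis open. Because 9.4.3 lists the mixed model as a separate option, it cannot be assumed to be what 9.4.2 means.

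A reader might infer two stronger points that the documents do not support.

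- **Any missed daily TUG removes a participant.** With seven daily sessions and 2% to 5% missed at each (assumed), 1 − 0.98⁷ = 13% to 1 − 0.95⁷ = 30% would be lost. But 9.4.2 models only day 1, day 7 and week 3, so a missed test on days 2 to 6 removes nobody. The synopsis attaches repeated measures over days 1 to 7 to exploratory outcomes, and that list omits TUG. Section 8.2 lists no sessions, which needs clarifying but does not specify a seven-session model.
- **The analysis is biased toward the ketogenic diet.** A simulation with no true effect, 16 per arm, SD 4 s, correlation 0.7 to 0.9, about 24% informative ketogenic-arm loss and 12.5% random control loss gives a completers-only day-7 bias of 0.36 to 0.55 s in that direction. The direction comes from the assumed asymmetry (Step 5). The plan also estimates the day-7 difference by the separate ANCOVA, and using all day-7 data brings the simulated bias close to zero.

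**Conclusion.** The point holds for the supporting TUG time-course analysis only. In its classical form the model in 8.2 and 9.4.2 excludes anyone missing day 1, day 7 or week 3, and week 3 is where gaps are most foreseeable. The cost in precision is modest: about 5% on the standard error at planned dropout and about 11% at the retention floor, assuming even loss across arms. Selection bias is possible if loss is informative, but neither its direction nor its size can be stated from the documents. The primary feasibility outcome, the sample size and the day-7 ANCOVA are untouched. The change is worth making because a better method is already named in 9.4.3 and costs almost nothing. If the sponsor already intends a likelihood-based fit under the repeated-measures label, the point reduces to saying so.

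**What to change.** In 8.2 and 9.4.2, replace repeated-measures ANOVA/ANCOVA for TUG with one likelihood-based linear mixed model, worded the same in both places:

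- **Outcome:** all observed post-baseline TUG values at the stated sessions (day 7 and week 3 under the present 9.4.2), from all randomised participants.
- **Terms:** session as a categorical factor, arm, arm-by-session, day-1 TUG and age.
- **Covariance and inference:** a prespecified structure (unstructured is feasible with two post-baseline sessions) and a small-sample degrees-of-freedom correction such as Kenward-Roger.
- **Off-schedule week-3 visits:** state whether and how they enter, for example within a stated window.
- **Missing day-1 TUG:** give a rule, since a missing covariate would still remove the participant.

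Keep the day-7 ANCOVA as the main secondary analysis. If days 2 to 6 are wanted in the time course, say so in both sections and choose a simpler covariance: seven post-baseline sessions unstructured would need 7 × 8 / 2 = 28 parameters from 32 participants.

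The cost is wording only, with no new data or visits. The small downside is reliance on data being missing at random given the observed values, and on the chosen covariance structure.
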